1.4 DISEASE BACKGROUND: BRAIN METASTASES AND LUNG CANCER

Lung cancer is the leading cause of worldwide cancer mortality, and is responsible for more deaths annually in the United States than the combination of breast, colorectal, and prostate cancer, with an estimated 1.04 million new cases each year worldwide[15,16]. Non-small cell lung cancer (NSCLC) accounts for approximately 75% of all lung cancers. Of these, approximately one third will develop brain metastasis at some time during the course of their disease. Brain metastases are a common problem in patients with metastatic NSCLC. About 7%–10% of NSCLC patients present with brain metastases at the time of initial diagnosis, and as many as 20%–40% of patients develop brain metastases at some point during their illness[17-20]. Additionally, 50% of all brain metastases are from lung primary tumors[21]. Unfortunately for the vast majority of these patients, this diagnosis is associated with significant morbidity in addition to shortened survival. Present treatments for brain metastases include surgery in select patients with limited intracranial and systemic disease burden and good performance status. However, the majority of patients receive treatment for their brain metastases via whole brain radiation Therapy (WBRT) and Stereotactic Radiosurgery (SRS). These modalities are often quite effective in alleviating symptoms; however, median survival remains poor, estimated to be between 2-7 months[22]. Clearly new treatments are needed.

Radiation is commonly utilized to treat brain metastases via WBRT or SRS. Generally speaking, SRS is utilized to treat a limited number of brain metastases while WBRT is utilized to treat more widespread disease. However, the definition of what constitutes limited versus widespread continues to evolve. WBRT can be conducted utilizing a number of different treatment machines and is most typically performed with a conventional linear accelerator. WBRT is given through a fractionated schedule with a typical regime being 30 Gy in 10 fractions. On the other hand SRS is conducted via a number of possible modalities including Gamma Knife or a conventional linear accelerator. Treatment is either as a single fraction or hypofractionated (within 3-5 fractions).

Therapeutic Agents Background: BINTRAFUSP ALFA (M7824) and Pimasertib

Refer to the Investigator's Brochure (IB)/approved labeling for detailed background information on Bintrafusp Alfa (M7824) and Pimasertib.

Background on Bintrafusp Alfa (M7824)

Bintrafusp Alfa (M7824) is a novel fusion protein comprised of the extracellular domain of the human TGF β -RII (transforming growth factor beta -receptor II) that is covalently linked to the C-terminus of the heavy chain of the anti-PD-L1 (anti-programmed death ligand 1) antibody via a flexible (Gly4Ser) 4G linker. The anti-PD-L1 moiety of Bintrafusp Alfa (M7824) is identical to anti-PD-L1 monoclonal antibody avelumab, except for 3 amino acid substitutions in the heavy chain constant regions that result in a different human IgG1 allotype, and one amino acid substitution in the heavy chain for antibody fusion protein stability. As of June 2017, FDA has granted accelerated approval to avelumab for metastatic Merkel cell carcinoma (MCC) and locally advanced or metastatic urothelial carcinoma whose disease progressed during or following platinum-containing chemotherapy.

The TGF β RII component functions as a TGF β neutralizing ‘trap’. Bintrafusp Alfa (M7824) is designed to target two negative regulatory pathways in immunosuppression: the cell-intrinsic one mediated by tumor cell-immune cell interaction, in which programmed death ligand-1 (PD-L1)/programmed

1.5 PIMASERTIB

Pimasertib is an orally bioavailable small-molecule inhibitor of MEK1 and MEK2 (MEK1/2) with potential antineoplastic activity. Pimasertib selectively binds to and inhibits the activity of MEK1/2, preventing the activation of MEK1/2-dependent effector proteins and transcription factors, which may result in the inhibition of growth factor-mediated cell signaling and tumor cell proliferation. MEK1/2 (MAP2K1/K2) are dual-specificity threonine/tyrosine kinases that play key roles in the activation of the RAS/RAF/MEK/ERK pathway and are often upregulated in a variety of tumor cell types.

Pimasertib (MSC1936369B) is an orally bioavailable and selective small-molecule inhibitor of MEK1 and MEK2 that prevents the activation of MEK1/2-dependent effector proteins and transcription factors [47, 48]. It has demonstrated robust antitumor activity in preclinical studies, including tumor growth reduction in murine myeloma xenografts [47] and tumor regression in a mouse model of D-MUT colorectal cancer [48] and it has also been shown to circumvent resistance to BRAF inhibition in human melanoma cells [47].

Pimasertib given as a single agent showed acceptable toxicity with a maximum tolerated dose (MTD) that depended on the treatment schedule in patients with advanced solid tumors [49]; with continuous twice daily administration, the MTD was 75 mg. When pimasertib was given in combination with FOLFIRI (5-fluorouracil/folinic acid/irinotecan), the MTD was reached at 45 mg/day in a 5 days on/2 days off schedule in patients with *KRAS*-mutated metastatic colorectal cancer [50].

2.0 RATIONALE FOR THE STUDY

2.1 RATIONALE FOR COMBINING IMMUNOTHERAPY WITH TARGETED THERAPY IN THE TREATMENT OF BRAIN METASTASES

Immunotherapies that target the interactions between antigen presenting cells (APCs), T lymphocytes, and cancer cells to potentiate an anti-tumor immune response have been developed, with many recently approved by the FDA for specific indications in many advanced malignancies. Over the past few years, immunomodulation has come to be a mainstay in the treatment algorithm in many malignancies, including melanoma and NSCLC, and a number of other cancers.

Nonclinical data show a negative association between MEK activity and active antigen presentation (MHC-1 and II expression) that appears to be coupled to simultaneous PD-L1 expression [51-52]. These findings link the MAPK pathway activation to the tumor immune-evasion. Consistently, MEK inhibition results in an increased number of tumor-infiltrating CD8-positive T lymphocytes and PD-L1 and MHC expression [51-52]. These effects are responsible for the enhanced anti-tumor immune response observed with the combination of MEK with PD-L1/PD-1 inhibitors [52].

The combination of a MEKi with immunotherapy has been studied in preclinical models and confirmed the presence of additivity if not synergy. The combination of cobimetinib and atezolizumab has also shown up to 50% ORR in patients with melanoma in a Phase I study and has now moved into the Phase III setting. IMspire is a Phase III study currently examining the combination of cobimetinib+atezolizumab vs pembrolizumab in patients with BRAF-wt melanoma (NCT03273153).

While there are number of trials looking into every possible combination of targeted therapies and IO, there is no clinical trial specifically in NSCLC has been matured yet. [57]

Standard Treatment for patients with oligo-brain metastases remains stereotactic radiosurgery. In recent years, immunotherapy and MEK inhibitors have shown intracranial activity in melanoma patients with brain metastases, raising question on whether such intracranial activity from immunotherapy and target agents can have sufficient intracranial activity to hold or delay SRS with the goal to minimize SRS treatment toxicity, without compromising patients' survival or intracranial control.

Pimasertib has excellent BBB penetration and can overcome one of the major issues facing other MEKis. Finally, using a bispecific PD-L1 and TGF β neutralizing 'trap' tackles 2 potential mechanisms of resistance to immunotherapy that are relevant for melanoma, breast, and lung cancers.

The goal of this combination is ultimately to seek synergy between MEK inhibition and the dual inhibition of PD-1/PD-L1 pathway and TGFbeta. It is also conceivable that potentiating the immune response, while augmenting tumor response, could also result in a higher rate of toxicities. At one level, immune-related toxicities could be augmented with specific attention being paid to pneumonitis and liver dysfunction. While the mechanism by which MEK inhibitors cause pneumonitis is distinct, it could still be perpetuated in the presence of an immune response. We will follow patients closely for those events and manage promptly. Another potential overlapping toxicity is uveitis. However, MEKi have been combined safely with anti-PD-L1 previously as in the Phase III study of cobimetinib+atezolizumab +/- regorafenib in colorectal cancer [58].

2.2 Rationale for combining immunotherapy with stereotactic radiosurgery (SRS) in the treatment of brain metastases

There is pre-clinical and clinical data suggesting clinical activity of systemic anti-neoplastic therapies, including immunotherapies and targeted therapies. One of the challenges of treating brain metastases is the blood-brain barrier leading to poor permeability of many drugs. The blood-brain barrier is a highly selective permeability barrier comprised of capillary endothelial cells, which are connected by tight junctions and astrocyte foot processes that limit diffusion of molecules and drugs into the CNS compartment [48, 49]. Additionally, as brain metastases tend to occur later in the disease course, these tumors may be biologically and genetically distinct from the primary site or extracranial metastatic sites and may be more resistant to cytotoxic and targeted therapies [50].

Radiation, in addition to providing effective local treatment through its tumoricidal effect via generation of DNA double strand breaks, has been found in recent years to trigger an immune response, leading to improved local control and abscopal effect (tumor regression in non-irradiated sites). This is achieved through radiation induced tumor neoantigen release, MHC class I expression, and pro-inflammatory cytokine release. Additionally, radiation has been found to modulate the immune suppressive tumor microenvironment by altering cell adhesion and immunomodulatory molecules and downregulating the suppressive cytokine effects. The best radiation regimen in inducing or supporting immune response is yet to be identified. Although stereotactic radiosurgery (SRS), which delivers high dose radiation in a single fraction was thought to generate the most robust immune response, recent pre-clinical study demonstrated that fractionated stereotactic radiation therapy (FSBRT), where radiation is delivered in 3-5 fractions, had better immune modulating effect through the STING pathway and induction of IFN- β . It would be of great importance to identify the best immune-promoting radiation regimen and to gain further knowledge on how radiation can interact with other CNS-penetrant small molecules to modulate tumor microenvironment and to enhance tumor killing.

3.0 STUDY DESIGN

This study is an open-label Phase I/II trial to determine the safety and efficacy of pimasertib in combination with Bintrafusp Alfa (M7824) in patients with brain metastases. The Phase I study will accrue patients with melanoma, lung, and breast cancers to a dose escalation phase as described below. The Phase II study will include expansion cohorts, of 10 patients each with melanoma, lung, and breast brain metastases, to better characterize the safety profile and efficacy of the combination and its impact on time to intracranial progression.

We have also incorporated an early imaging time point to allow the application of SRS to intracranial lesions that are either progressing or not responding. This decision will be made in the context of multi-disciplinary care provided at the MD Anderson Brain Metastasis Clinic.

[figure not shown]
Phase I:

The phase I dose finding part of the study is to determine the recommended phase II dose (RP2D) of Bintrafusp Alfa (M7824) + pimasertib in patients with intracranial metastasis. The planned DL1 and DL2 doses are Bintrafusp Alfa (M7824) flat dose of 1200 mg every 2 weeks and pimasertib 45 mg PO BID (Dose Limit or DL1) and 60 mg PO BID (DL2), and fallback doses DL-1 are Bintrafusp Alfa (M7824) flat dose of 1200 mg every 2 weeks and Pimasertib at 30 mg PO BID. Every cycle will be 28 days. We will enroll up to 12 patients to the Phase I portion (18, should the trial de-escalate to DL-1). The standard “3+3” design will be employed to determine the RP2D. If DL1 is considered too toxic, DL-1 will be explored; if unacceptable toxicity is observed at DL-1, alternative dose schedules may be evaluated in an amendment. The recommended phase II dose (RP2D) is defined as the highest dose level with no more than 1 patient with DLT out of 6 patients that are treated. Please note that the study plans on enrolling up to 2 cohorts in Phase 1 of the trial (the 45mg and either the 30 or 60 mg, depending on the safety of Cohort 1).

Phase II:

The purpose of phase II part is to estimate the time to intra-cranial progression and overall survival time. In this part, we will enroll up to 24 patients into RP2D. The 6 patients treated at RP2D from phase I part of the study will be included in the Phase II part, thus resulting in a total of 30 patients at RP2D by the end of the study, with the goal of having 10 patients each of melanoma, NSCLC, and breast cancer. This phase II part is designed to collect data for future larger studies. Specifically, we would like to estimate time to intracranial progression considering death as a competing risk and overall survival time using Kaplan-Meier method, both with 95% confidence interval.

Figure 1: Study Schema

[Study Schema] – See Schedule of Assessments

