Recent advances in targeted and immunotherapy of melanoma have led to intracranial responses with systemic therapy. Targeted therapy with BRAF/MEKi leads to a high rate of intracranial responses similar to extracranial disease albeit of seemingly shorter duration. Immunotherapy with combination anti-CTLA4 and anti-PD-1 antibodies has led to high response rates in patients with melanoma brain metastases that have the following characteristics: a) clinical responses as early as 6 weeks, b) complete responses in 26% and overall objective response rate in 56% of patients, c) durability in >90% of patients, d) high concordance between extracranial and intracranial disease, and e) high progression free survival rates of >60% at one year. [53, 54].

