6.2.8 PERMITTED THERAPIES: SRT

For patients that are deriving clinical benefit from protocol treatment, but having evidence of progression in brain lesions that are amenable to SRS, treatment with SRS is allowed and patients can remain on systemic therapy. Patients will be censored for brain metastasis response unless one measurable lesion remains unirradiated. Patients will continue to be monitored for intracranial PFS.

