9.3.2 INTRACRANIAL PROGRESSION FREE SURVIVAL

The time to intracranial progression, determined by modified RECIST 1.1, will be calculated from the time of study enrollment to intracranial progression (event) or the last follow-up date if the patient has not developed the intracranial progression yet (censored). The median time to intracranial progression and intracranial progression free survival rates at specific times will be estimated and reported with 95% confidence interval utilizing the method of Kaplan and Meier. This will serve as the primary analysis and will be performed overall and within each treatment group. Completing risk analysis may be considered by treating events outside of intracranial disease progression (e.g. events such as extracranial disease progression, early dropout due to toxicity, or death) as competing risks.

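### Radiosurgery given before RECIST progression has no rule in the primary endpoint, so time to intracranial progression mixes drug and SRS effects in those patients

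*Combined protocol and SAP*

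**What the plan says.** Section 3.0, repeated in the synopsis, builds in an early imaging time point to "allow the application of SRS to intracranial lesions that are either progressing or not responding", with the decision left to the multidisciplinary clinic. Lack of response is not defined there.

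Section 6.2.8 is narrower. It concerns patients who benefit from treatment while "having evidence of progression in brain lesions that are amenable to SRS, treatment with SRS is allowed and patients can remain on systemic therapy". It then gives two follow-up rules. For response: "Patients will be censored for brain metastasis response unless one measurable lesion remains unirradiated". For progression: "Patients will continue to be monitored for intracranial PFS".

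Time to intracranial progression is a phase II primary objective (Section 4.1.2), together with overall survival. Section 9.3.2 has it "calculated from the time of study enrollment to intracranial progression (event) or the last follow-up date", estimated by Kaplan-Meier as the primary analysis. SRS is not an event there, nor a reason for censoring, nor one of the example competing events (extracranial progression, dropout for toxicity, death). Section 4.2 lists time to second intracranial progression after salvage SRS as a secondary objective. Section 2.1 asks whether immunotherapy and targeted agents "can have sufficient intracranial activity to hold or delay SRS" without compromising survival or intracranial control.

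**The concern.** Under Appendix 2, a patient whose brain lesions have neither shrunk nor grown enough has stable disease, which is not a primary event. Section 3.0 appears to let such a patient receive SRS at the early scan. Section 9.3.2 then keeps the clock running, and whatever local control SRS provides lengthens the recorded time to intracranial progression. The more freely SRS is used before progression, the better the primary result looks.

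Phase II is a single-arm estimate from 30 patients, meant to inform larger studies. With no control arm and no record of why SRS was given, a later reader could not separate the part of the figure due to the drugs. This also fits poorly with the question in Section 2.1: a patient who needed early SRS for lack of response is counted in the same way as one in whom SRS was successfully held off.

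**Working it through.** **1. Which patients are affected.**

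- *SRS after a first modified-RECIST progression.* Section 9.3.2 makes that progression the event. Later time belongs to the second-progression objective in Section 4.2. The primary endpoint is not affected.
- *SRS to a stable lesion.* Allowed by Section 3.0 and the synopsis, not described in Section 6.2.8. There is no event at SRS, and Section 9.3.2 counts on to progression or last follow-up. Affected.
- *SRS to one growing lesion while the sum stays below the threshold.* Appendix 2 requires at least a 20% rise and at least 5 mm in the sum of target diameters from nadir. Example with assumed lesions of 20, 15, 12, 8 and 6 mm: the last grows to 10 mm, which is (10 - 6)/6 = +67%. The sum goes from 61 to 65 mm, which is +4 mm and 4/61 = +6.6%. By target measurements this is not progression, yet Section 6.2.8 could be read as allowing SRS. Affected, even under the narrower section.

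**2. When it could happen.** Table 3 places the first on-study MRI at Cycle 2 Day 1, which is week 4.

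**3. Size.** The plan states no figure to reproduce and gives none of the inputs, so this is an illustration. Assumptions: exponential time to intracranial progression on drug alone with median m = 4.0 months; SRS at day 28 (s = 0.92 months) to a fraction f of those still progression-free; hazard multiplied by h afterwards for all intracranial progression.

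With λ = ln 2 / 4.0 = 0.1733 per month, for t > s:

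S(t) = exp(-λs) × [(1 - f) exp(-λ(t - s)) + f exp(-λh(t - s))]

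Progression-free at day 28: exp(-0.1733 × 0.92) = 0.853. Irradiated before progression: 30 × 0.853 × 0.2 = 5.1 to 30 × 0.853 × 0.4 = 10.2 patients.

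| f | h | median as written (months) | 6-month progression-free |
|---|---|---|---|
| none | – | 4.0 | 35% |
| 0.2 | 0.7 | 4.2 | 37% |
| 0.2 | 0.5 | 4.4 | 39% |
| 0.2 | 0.3 | 4.6 | 41% |
| 0.4 | 0.7 | 4.4 | 40% |
| 0.4 | 0.5 | 4.9 | 43% |
| 0.4 | 0.3 | 5.5 | 47% |

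If SRS before progression counts as an event, the 6-month figure is (1 - f) × 0.354, which is 28% for f = 0.2 and 21% for f = 0.4.

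**4. Sensitivity to timing.** If SRS falls at or after the drug-only median, the median does not move. With m = 8 weeks and SRS at week 8 it stays at 8.0 weeks. Later rates still rise: over f = 0.2-0.6 and h = 0.3-0.7, the 24-week proportion is 0.14-0.25 against 0.125.

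**The case against.** The strongest reply is that Section 6.2.8 is the operative treatment section and ties SRS to progression. If it governs, most of the mixing disappears. A reader might also infer that its sentence on continued monitoring for intracranial PFS deliberately keeps stable-disease patients in the count. It does not address them: its premise is progression, and for other patients the continued counting follows from the silence of Section 9.3.2. Nor is SRS at progression a serious gap, because the second-progression objective presupposes that the earlier progression was the first event. What stands against the reply is that Section 3.0 and the synopsis still say something wider, and that one lesion can progress without the sum doing so.

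Following patients through SRS is also a legitimate treatment-policy approach, and Section 2.2 gives a rationale for combining immunotherapy with SRS. That stands. The fault is that the plan neither declares the approach nor accompanies it with an analysis closer to the question in Section 2.1. Reading early SRS as a failure on that question is an interpretation, not protocol text.

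Three stronger readings are tempting and unsupported.

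- *The trial cannot measure drug activity in the brain.* Intracranial response is a secondary endpoint, and Section 6.2.8 censors it at SRS unless a measurable lesion remains unirradiated.
- *Many patients will count as non-responders at week 4, because responses come* "clinical responses as early as 6 weeks". That background statement is about anti-CTLA4 plus anti-PD-1 in melanoma. It says nothing of this regimen or of the lung and breast cohorts, and the frequency is unknown.
- *The primary estimate is known to be inflated by a given amount.* Every input is assumed. The model applies the SRS benefit to new and unirradiated lesions, which focal treatment does not reach, and gives irradiated patients the average hazard.

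Finally, phase II has no hypothesis or efficacy decision rule, and precision is low. If all 30 patients progress, the approximate exponential 95% interval around 4.0 months is 4.0 × exp(±1.96/√30), or 2.8 to 5.7 months, which contains the whole illustrated shift. That lowers the priority. It does not remove a bias that runs in one direction.

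**Conclusion.** The point holds for patients irradiated before a first modified-RECIST progression, and only for them. The design section and the synopsis disagree with Section 6.2.8 on when SRS may be given, and the primary endpoint is silent on SRS before progression. As written, the estimate would combine drug and SRS effects in those patients, toward longer apparent control. The amount cannot be known from the documents. The illustrated median of about 4.2-5.5 months against 4.0 rests on the stated assumptions, and the shift shrinks toward zero if few patients are irradiated early or if SRS does little for the rest of the brain. This should be fixed, because the estimate is what phase II is for and the repair is cheap. It is not a defect that invalidates the study.

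**What to change.** 1. Reconcile Section 3.0 and the synopsis with Section 6.2.8 on when on-study SRS may be given. If lack of response remains a ground, define it. The clinical choice is the sponsor's.
2. In Section 9.3.2, state that the primary analysis follows patients through SRS (treatment policy). State also that a progression triggering SRS is the event, dated to that MRI, and that later SRS does not reset it. This is mostly clarification.
3. Add a companion analysis: time to intracranial progression or first on-study SRS or brain surgery to a lesion without prior RECIST progression, with that local therapy counted as an event. Simple censoring at SRS is not a good substitute, because the choice to irradiate probably depends on prognosis.
4. Record date, lesion and reason (progressing or not responding) for each SRS on the eCRF, and report how many patients had it before progression and when. Do this prospectively, since reasons may be hard to recover later.

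The cost is protocol wording, one eCRF field and one extra analysis, with no added patients or scans. The companion figure will be less favourable than the primary one whenever pre-progression local therapy occurs. It also counts a clinical decision as an event, so it should be read beside the primary analysis and not in place of it.
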